Referral to colposcopy guidelines are in accordance with planned NSU recommendations with the additional safety that patients with low grade cytology and hrHPV other who will be referred to colposcopy.

Referral to colposcopy is indicated for patients with a significant risk of high-grade cervical abnormalities. The recommendations in this pilot study have been agreed with the NCSP and take into consideration the current recommendations for colposcopy referral, risk of CIN2+, colposcopy service capacity, access to colposcopy for underserved populations, and the requirement of data collection from this study in a timely manner to inform implementation of the NCSP. It is important to acknowledge that these recommendations may differ to the final NCSP recommendations and time frames on the basis of this and other information yet to be determined.

Patients with hrHPV other and low-grade cytology are referred to colposcopy in this study because the burden of disease in this group is not documented in NZ. Within this study we are unable to follow up this group via repeated testing, in addition patients over 30 with low grade cytology and hrHPV are currently referred to colposcopy and laboratories are obliged to put this advice on their cytology reports. It is anticipated in the new program that these patients will undergo repeat testing at 12 and 24 months as per the Australian program.

Risk of CIN2+ can be stratified as below:

Low risk

- Other HPV positive, cytology normal or unknown

Intermediate risk

- HPV 16/18 positive with normal cytology
- Other HPV with ASCUS/low grade cytology (the risk for this group in NZ is unknown and may be low)

High risk

- HPV 16/18 positive with ASCUS/low grade/high-grade/AGC cytology
- Other HPV with high-grade/AGC cytology

Patients stratified as low risk will be recommended to have a repeat screen in 12 months.

Patients with intermediate risk will be referred to colposcopy as a semi urgent referral (for the purpose of the study we request these patients are seen within 3 months).

Patients with HPV 16/18 who do not undergo cytology may be referred as high risk because their risk is undetermined and may be high risk.

Patients with high risk of CIN2+ are referred for colposcopy (20 working days).

Patients with suspected cancer will be seen within 10 working days and treated accordingly as per regional practice.

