Appendix 1 *Data Management Plan (see separate document)*

Appendix 2 Safety and quality assurance plan

Introduction

This study is performed to determine the impact of implementation of hrHPV testing into the NCSP. The aim of screening is to prevent cervical cancer by the identification and treatment of the precursors to cervical cancer. While the NCSP has been a highly successful public health intervention, screening has its limitations and for individual screening failure can occur, this may be due to the inherent weaknesses of the test, diagnostic and treatment pathways, or failure of the process to be carried out correctly. It is well documented that the major cause of screening failure is non-engagement with the screening program, however, failure of the screening test to detect an abnormality and failure of the diagnostic and treatment pathway are also associated with a significant number of cancer occurrences. In addition, there are a number of service delivery interactions that may significantly affect the quality of a patient's experience which may in turn have an impact on future participation. It is well documented that the impact of these failures is inequitable.

The introduction of hrHPV testing will be associated with an increased sensitivity of the screening test and offers greater accessibility of the test and hence will improve the safety of the program. However, the change in procedures may increase, at least temporarily, the possibility of procedural or administrative errors. It is therefore important to monitor patient safety aspects of this study. This will be done by reporting adverse events, site visits, and auditing of data against source documents.

Identified risks

Major risks

Failure to detect significant abnormality (false negative test)

Patient given wrong result

Patient given inappropriate advice

Patient not informed regarding a positive result

Colposcopy for high grade cytology or HPV 16/18 not attended within 3 months

Inequity associated with participation

Other risks

Eligible patients not invited

Minimum invitation requirements not met

Patient positive for other hrHPV (i.e., non-HPV16/18) does not attend for cytology

Patient with other hrHPV (i.e., non-HPV16/18) does not attend for colposcopy

Serious adverse event reporting

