Serious adverse events will be reported to the study management team by filling out a Serious Adverse Event (SAE) report form and emailed within 7 days of the GP practice becoming aware of the event.

Serious Adverse Events include:

- Interval diagnosis of invasive cancer, CIN3, or AIS following a negative hrHPV test
- A screened person being given the wrong result
- A screened person being given the wrong advice following their screen (e.g., not referred to colposcopy or cytology when they should have been)
- A screened person not receiving the result of a positive test

Serious adverse events will be investigated as soon as possible by the study team and the relevant service provider to ensure similar errors do not occur and that there is no systemic case for this error.

The service provider will be responsible for the discussion of this adverse event with the person affected and their whanau and informing other agencies if appropriate. The study team will be responsible for informing the NCSP.

The following other adverse events will also be reported at completion of the study

- A person referred to colposcopy who does not attend within 3 months
- A person with other hrHPV who is recommended to have cervical cytology but who does not attend within 3 months

Site visits

Site visits will be performed either face to face or virtually by at least 1 member of the study management team, prior to commencing invitation to the study and within 3 months of commencing the study. Additional visits will be organised on request of the participating practice or if issues are perceived by the study management team.

The first visit is to ensure mechanisms of enrolment data management and clinical management of patients is understood by all members of the team. In addition, to ensure that systems are appropriate.

The second visit is to understand any issues of concern being encountered by the practice and to ensure ongoing participation of the practice team with screening and study protocols.

Further site visits may occur as required if areas of concern have been identified.

Audit

Prospectively-collected data will be collected in electronic case report forms (e-CRF) within 4 weeks of the event. 10% of data will be audited against source documents. If more than 10% of data is missing or incorrect, further in-depth audit will be undertaken.

Quality assurance

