Appendix 6 Flowchart for management of hrHPV results either clinician taken or vaginal self-test

*Note if a vaginal self-test is taken and the result is positive a cervical cytology specimen is indicated to stratify risk, however in some circumstances it will not change so is

not required. (i.e. HPV16/18 positive) If a cervical test has been taken this will be performed on the same specimen by the laboratory. It is advised that this test is performed within 2 weeks.

**With the new five yearly screening interval, those coming in for their next screening test (after previous cytology screening) any time in the last five years before age 69, i.e. 65 – 69 years of age (inclusive), can exit the programme if their hrHPV test result is negative. This includes those with normal screening histories, with no screening history and those with previous abnormalities who have already been returned to regular interval (three yearly) screening. Exceptions are:

1. Participants who are still in active surveillance following previous abnormalities need to complete their follow-up. So if a test of cure is indicated and hasn't been successfully completed then they need a test of cure – one negative HPV test is not sufficient in this circumstance.
2. Immune deficient participants with a negative hrHPV test need to return in three years for a repeat hrHPV screen, if this falls before 69 years of age
3. Women who have had a recent hysterectomy will need a test of cure if there is high-grade histology in the hysterectomy specimen, which may or may not have been preceded by high-grade cytology.

[figure not shown]
Those who would normally exit the NCSP under the current NCSP exit requirements i.e. have had two normal screening cytology samples between ages 62 and 69 years of age, can exit at 69 years of age without HPV testing (providing not immune deficient or requiring further follow-up because of abnormal results).

***Urgency of referrals to Colposcopy are as follows;

- **Very Urgent** – Suspicion of Malignancy (10 working days)
- **Urgent** – High-grade cytology and/or HPV 16 or 18 positive (20 working days)
- **Semi-Urgent** – other high-risk HPV and low-grade/ASCUS cytology (3 months)
- Colposcopy can be referred as a clinical override e.g. hrHPV other and patient declining cytology triage.

ASCUS: Atypical Squamous Cells of Undetermined Significance hrHPV: high risk human papillomavirus NCSP: National Cervical Screening Programme

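### The colposcopy non-attendance event in Appendix 2 uses one 3-month window that does not match the protocol's shorter urgency targets, and a risk ranked as major is reported only at study completion

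*Protocol*

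**What the plan says.** **Targets.** The Referral to colposcopy section gives waiting times by risk. For suspected cancer: "Patients with suspected cancer will be seen within 10 working days". For the high-risk group: "Patients with high risk of CIN2+ are referred for colposcopy (20 working days". Intermediate-risk patients are to be seen within 3 months. The Appendix 6 legend repeats the three tiers, with "Suspicion of Malignancy (10 working days" for the very urgent class, 20 working days for high-grade cytology and/or HPV 16 or 18, and 3 months for other hrHPV with low-grade or ASCUS cytology.

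**Risk ranking.** Appendix 2, Identified risks, lists among the major risks "Colposcopy for high grade cytology or HPV 16/18 not attended within 3 months". Non-attendance at colposcopy by patients with other hrHPV is listed separately, under other risks.

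**Event reporting.** Serious adverse events are to be "emailed within 7 days of the GP practice becoming aware of the event", and are then investigated for a systemic cause. Colposcopy non-attendance is not on that list. It comes under a later sentence, "The following other adverse events will also be reported at completion of the study", as "A person referred to colposcopy who does not attend within 3 months", with no distinction by urgency.

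**Other oversight.** Scheduled site visits take place "prior to commencing invitation to the study and within 3 months of commencing the study", with further visits allowed if concerns arise. The Quality assurance part of Appendix 2 has REDCap remind the practice and the study team about individual patients, including colposcopy attendance within time frames that the protocol does not give. The Outcome measures section reports time from referral to colposcopy by urgency class, in those who had a colposcopy.

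**The concern.** The event window equals the target of the least urgent referred class. For the two more urgent classes it is several times longer than the time in which the protocol says they should be seen. A patient with suspected cancer or high-grade cytology who attends at week 12 has missed the protocol's own target by weeks, yet does not enter the adverse event count.

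The risk ranking and the reporting route also do not line up. A risk classed as major shares one event with a risk classed as lower, and the reporting time is the end of the study. The event count could therefore say little about timeliness in the patients at highest risk, and an aggregate picture of that risk would come only after care in the study is over. The Background calls access to cytology triage and colposcopy an important focus of the study and names delayed specialist assessment as a source of inequity, so this is not a side issue.

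**Working it through.** **1. Window against target.** Take 3 months as 13 weeks × 5 = 65 working days.

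| Class | Target | Event window ÷ target |
|---|---|---|
| Very urgent | 10 working days | 65 / 10 = 6.5 |
| Urgent | 20 working days | 65 / 20 = 3.25 |
| Semi-urgent | 3 months | 1 |

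Attendance between working day 10 and about day 65 (very urgent), or between day 20 and about day 65 (urgent), is late by the protocol's target but is not an event.

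**2. Major risks against serious adverse events, both in Appendix 2.**

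| Major risk | Counterpart on the serious adverse event list |
|---|---|
| False negative test | Interval cancer, CIN3 or AIS after a negative test |
| Wrong result given | Yes |
| Inappropriate advice | Yes |
| Positive result not communicated | Yes |
| Late colposcopy, high-grade cytology or HPV 16/18 | None; reported at completion |

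The sixth major risk, inequity in participation, is not a patient-level event. Of the five that are, only late colposcopy lacks a counterpart.

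**3. Timing of scheduled oversight.** The second scheduled visit falls within 3 months of starting. A 3-month non-attendance event needs a referral made after the start plus 3 months, so none can have matured by then. The audit checks data against source documents, not attendance.

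**4. How many referrals are affected.** Appendix 4 states 26 urgent and 18 semi-urgent referrals per 1000 screened, 44 in all. From its own inputs (7% positivity, 25% HPV 16/18, and for other hrHPV 45% normal and 35% low-grade cytology, leaving 20% high-grade):

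- HPV 16/18: 70 × 0.25 = 17.5 (stated 18).
- Other hrHPV, high-grade: 70 × 0.75 × 0.20 = 10.5 (stated 8).
- Urgent total: 17.5 + 10.5 = 28 (stated 26).
- Semi-urgent: 52.5 × 0.35 = 18.4 (stated 18).

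The urgent total comes out close to the stated figure, although the component of 8 does not reproduce. If HPV 16/18 with normal cytology (30% of that group) is moved to semi-urgent, 26 − 17.5 × 0.30 = 20.75, which matches the stated 21.

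For 3000 screened, on the stated figures:

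- Urgent: 21 × 3 = 63 to 26 × 3 = 78.
- All modelled referrals: 44 × 3 = 132.
- Urgent share: 63/132 = 48% to 78/132 = 59%.

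With the recomputed 28 per 1000 the urgent number is 84. Over the protocol's 5 to 10% positivity range it is (50 × 0.25 + 50 × 0.75 × 0.20) × 3 = 60 to (100 × 0.25 + 100 × 0.75 × 0.20) × 3 = 120.

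**5. What cannot be computed.** The protocol gives no rate of delay or non-attendance and no expected number of suspected cancers, so the number of missed targets is unknown.

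**The case against.** The strongest reply is that a waiting-time target and a non-attendance event serve different purposes and may have different windows. Appendix 2 uses 3 months both in its risk list and in its event, so it is consistent with itself on the window, and 3 months may have been deliberate. That stands as far as it goes: the window is not shown to be a slip. It does not explain why the one patient-level major risk without a serious adverse event counterpart shares an event with a lower-ranked risk.

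The second reply is that the study does watch these patients. REDCap reminders go to the central team as well as the practice. The study team follows all patients to the end of the study to see that those needing colposcopy have been seen. The main Quality assurance section lists assessment at cytology and colposcopy among monitored items. The primary objectives include completion of each pathway step and time to completion. All of this is real mitigation. But the reminders concern individual patients, their time frames are not stated in the protocol (the separate Data Management Plan may hold them), and no measure, frequency or trigger is attached to aggregate monitoring. The waiting-time outcome covers attenders only and gives mean, median and range, not the proportion seen within target.

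A reader might go further and infer that missed urgent targets never become events, or that no pattern could be acted on. The documents do not support either. An urgent patient still unseen at 3 months is an event, and the reminders and optional visits allow action during the study.

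The denominator of 132 also omits referrals outside the Appendix 4 model, such as test-of-cure patients and other hrHPV patients referred without cytology, so the urgent share is approximate.

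**Conclusion.** The point holds as a mismatch within the protocol and a gap in aggregate oversight, not as an absence of safety monitoring. The event window is about 3.3 times the urgent target and 6.5 times the very urgent one, so late attendance before 3 months in those classes is not counted as an adverse event. The late-colposcopy risk that Appendix 2 ranks as major is reported only at completion, in an event shared with lower-risk referrals, and no aggregate review during the study is written down.

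About 63 to 78 of about 132 modelled referrals, roughly half or somewhat more, are in the urgent class. This assumes 3000 screened and Appendix 4's stated rates. The lower figure treats HPV 16/18 with normal cytology as semi-urgent and the higher treats it as urgent. The protocol is itself in conflict here: the Referral to colposcopy section puts that group at intermediate risk, to be seen within 3 months, while the Appendix 6 legend makes any HPV 16 or 18 positive result urgent at 20 working days. No claim is made about how many patients would miss a target, or about which time limit is clinically right.

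**What to change.** 1. Reconcile the Appendix 2 event with the urgency targets in the Referral to colposcopy section and Appendix 6, and resolve the conflict between those two on HPV 16/18 with normal cytology. Which limits apply is a matter for the sponsor and the screening programme.
2. Alongside the existing 3-month event, count by urgency class the referrals not seen within whatever target the reconciled protocol states.
3. Report the major-risk group named in Appendix 2 (high-grade cytology or HPV 16/18) separately from other hrHPV.
4. Tabulate these counts by practice at set intervals during the study, and use the table to inform the extra site visits that Appendix 2 already allows.

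**Cost.** Revised wording in Appendix 2 and a periodic REDCap query. Referral urgency and the dates needed are already implied by the planned waiting-time outcome and the 3-month event. There are two downsides. More events will be counted, so the safety report will look less favourable. Because data entry may lag an event by up to 4 weeks, a recent table may show patients as unseen who have in fact attended. The latest counts should be marked provisional and updated in the next table.

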Appendix 3 Risk assessment by hrHPV and Cytology result

The risk of CIN2 + by hrHPV and cytology.^{15, 16}

History	Current HPV result	Current cytology result	n	%	CIN 3+ cases	CIN 3+ immediate risk, %	CIN 3+ 5-year risk, %	Recommended Management	Recommendation confidence score, %
Unknown	HPV-negative	NILM	1,388,153	90	1,246	0.00	0.12	5-y follow-up	100
Unknown	HPV-negative	ASC-US	25,331	1.6	83	0.04	0.40	3-y follow-up	100
Unknown	HPV-negative	LSIL	3,300	0.21	47	1.1	2.0	1-y follow-up	100
Unknown	HPV-negative	ASC-H	791	0.05	26	3.4	3.8	Colposcopy ^d	Special situation
Unknown	HPV-negative	AGC	2,275	0.15	27	1.1	1.5	Colposcopy ^d	Special situation
Unknown	HPV-negative	HSIL+	183	0.01	43	25	27	Colposcopy/treatment	53
Unknown	HPV-negative	ALL ^b	1,420,033	92	1,472	0.01	0.14	5-y follow-up	95
Unknown	HPV-positive	NILM	63,541	4.1	1,798	2.1	4.8	1-y follow-up	100
Unknown	HPV-positive	ASC-US	30,506	2.0	1,378	4.4	7.3	Colposcopy	100
Unknown	HPV-positive	LSIL	23,659	1.5	1,008	4.3	6.9	Colposcopy	96
Unknown	HPV-positive	ASC-H	3,766	0.24	863	26	33	Colposcopy/treatment	82
Unknown	HPV-positive	AGC	977	0.06	254	26	35	Colposcopy/treatment ^d	80
Unknown	HPV-positive	HSIL+	3,980	0.26	1,700	49	53	Colposcopy/treatment	100
Unknown	HPV-positive	ALL ^b	126,429	8	7,001				
		Total ^f	1,546,462	100	8,473				

	Total	CIN3+			CIN2+				
		N (cases)	Risk	95%CI	N (cases)	Risk	95%CI		
All HPV positive ^a									
ASC-US	717	154	21.5	18.7	24.7	223	31.1	27.9	34.6
LSIL	333	99	29.7	25.2	35.0	146	43.8	38.7	49.4
High-grade ^b	554	359	64.8	60.9	68.8	397	71.7	67.9	75.4
≥ASC-US	1604	612	38.2	35.8	40.6	766	47.8	45.3	50.2
HPV16									
ASC-US	132	51	38.6	30.9	47.5	63	47.7	39.6	56.6
LSIL	79	37	46.8	36.6	58.4	49	62.0	51.5	72.6
High-grade	189	143	75.7	69.4	81.5	153	81.0	75.1	86.2
≥ASC-US	400	231	57.8	53.0	62.6	265	66.3	61.6	70.9
HPV18									
ASC-US	53	11	20.8	12.1	34.3	18	34.0	22.9	48.4
LSIL	22	6	27.3	13.3	50.9	11	50.0	31.6	71.8
High-grade	52	34	65.4	52.6	77.9	38	73.1	60.7	84.2
≥ASC-US	127	51	40.2	32.3	49.2	67	52.8	44.4	61.6
Other high-risk HPV ^c									
ASC-US	498	90	18.1	15.0	21.7	138	27.7	24.0	31.9
LSIL	225	55	24.4	19.4	30.6	84	37.3	31.4	44.0
High-grade	294	174	59.2	53.6	64.8	198	67.4	62.0	72.6
	Total	CIN3+ N (cases)	Risk	95%CI	CIN2+				
					N (cases)	Risk	95%CI		
Baseline HPV Result									
HPV-positive ^a	1278	102	8.0	6.6	9.6	154	12.1	10.4	14.0
HPV16	201	40	19.9	15.0	26.1	49	24.4	19.0	30.9
HPV18	74	8	10.8	5.6	20.5	12	16.2	9.6	26.8
Other high-risk HPV ^b	981	54	5.5	4.2	7.1	92	9.4	7.7	11.4

HPV-based Screening Implementation Study Protocol

Without triage

HPV negative	cytology unknown	risk of CIN3	0.01%
HPV positive	cytology unknown	risk of CIN3	6%

With triage

HPV 16	normal cytology	risk of CIN2+	24%
HPV 16	ASCUS	risk CIN2+	47%
HPV 16	HSIL	risk CIN2+	81%
HPV other	normal cytology	CIN2+	9.4%
HPV other	ASCUS /LSIL	CIN2+	28%/37%
HPV other	HSIL	CIN2	67%

Data is limited from New Zealand. Rates vary from different populations and age groups and studies and rates of CIN3 are lower. However, patterns remain constant across studies. CIN3 has a greater risk of progression to cancer and a lower rate of spontaneous regression.

While to some extent it can be argued that all patients who are hrHPV positive should undergo colposcopy, these resources in NZ are limited and cytology triage is appropriate to limit the number of referrals and urgency. Low risk patients can safely be monitored with repeat tests and intermediate risk patients may be safely managed with non-urgent colposcopy. Australian data suggests that patients with other hr HPV and low-grade cytology have a low risk of CIN2+ (similar to the risk for patients with normal cytology). As a result, Australian guidelines recommend follow up hrHPV tests for 2 years prior to referral to colposcopy. As this is inconsistent with data from NZ and Europe and we have no data on completion of follow up, we aim to document the proportion of patients with CIN2+ in this group following referral to colposcopy.

HPV screening data is limited in NZ and this pilot study aims to acquire data on real world hrHPV screening in New Zealand and the utility of cytology triage in a program utilising self-testing. As such, we propose that all hrHPV positive patients are recommended to undergo cytology triage. However, it is acknowledged that for some patients this will represent a barrier and therefore in some circumstances it may be appropriate to refer to colposcopy without a cytology triage. These circumstances may include unscreened patients, patients unable or unwilling to undergo speculum examination, and populations at increased risk. If referral without cytology triage occurs, triage will take place on the basis of the hrHPV result and circumstances will be documented.

